2.1 Trial Rationale

The purpose of this trial is to determine the absorption, metabolism, and excretion of (¹⁴C)-OPC-61815 and to characterize and determine the metabolites present in plasma, urine, and, where possible, feces in healthy male Japanese subjects following a single intravenous (IV) dose. Knowledge of the absorption, metabolism, and excretion of parent drug and identification/characterization of its metabolites is useful for evaluating the Metabolites in Safety Testing requirements elucidated in the International Conference on Harmonisation M3² and the likelihood of effects of renal or hepatic impairment on the disposition of OPC-61815 and the likelihood for drug-drug interactions with OPC-61815.

2.2 Background

OPC-61815 is a compound for which the low water solubility of OPC-41061 has been improved by phosphorylation of the hydroxide of the benzazepine ring. In the body, OPC-61815 is thought to be metabolized to OPC-41061 via hydrolysis of the phosphate ester by alkaline phosphatase and acid phosphatase.

2.3 Summary of Nonclinical Pharmacokinetics

The pharmacokinetics (PK) of OPC-61815 following single IV dosing were investigated in nonfasting rats and dogs. In both species, the plasma concentrations of OPC-61815 (disodium salt [free form]) and its active metabolite OPC-41061 increased dose-dependently. The extrapolated plasma concentration at time zero (C₀) and the area under the concentration-time curve (AUC) from time zero to infinity (AUC_∞) of OPC-61815 (free form) in male rats were both 1.6 times higher than those in female rats. A sex difference in the plasma concentration-time course of OPC-41061 was observed, with the maximum peak concentration of the drug (C_{max}) and AUC_∞ in female rats being respectively 2.4 and 5.8 times higher than those in male rats, indicating a higher plasma

concentration in females. In dogs, the C_0 and AUC_{∞} of OPC-61815 (free form) in males were both 0.6 times those in females, while no clear sex difference was observed for OPC-41061. In both species, OPC-41061 was detected in plasma at 5 minutes postdose, indicating rapid hydrolysis from OPC-61815 to OPC-41061.

Following a single IV dose of (^{14}C)-OPC-61815 at 12.75 mg/kg to male rats, radioactivity was distributed into the liver, small intestine, kidney, and adrenal gland at higher levels than the plasma C_{\max} . Although, the plasma concentration of radioactivity was lower in female rats than in male rats, no sex differences were observed in the tissue concentrations of radioactivity. At 168 hours postdose, the concentrations of radioactivity were below the lower limit of quantification in almost all tissues. As a result of quantitative autoradiography in pregnant rats, radioactivity concentrations in all fetal tissues were comparable to or lower than the blood concentration in the dams, indicating low transfer of OPC-61815 to fetuses.

The distribution of radioactivity to blood cells was 1.24% to 14.69% in male rats, 1.40% to 26.04% in female rats, and 0.49% to 18.03% in male dogs, indicating low distribution to blood cells in both species.

Following a single IV dose of OPC-61815 to male rats and dogs, in rats, the AUC_{∞} of the metabolites DM-4103 and DM-4107 were respectively 1.5 to 4.0 times and 0.17 to 0.62 times that of OPC-41061, and in dogs, the plasma concentrations of DM-4103 and DM-4107 were both lower than that of OPC-41061.

When (^{14}C)-OPC-61815 was incubated with human liver, kidney, lung, and small intestine 9000 g supernatant fractions (S9), OPC-61815 underwent hydrolysis to OPC-41061. OPC-61815 also underwent hydrolysis to OPC-41061 when incubated with human-derived acid phosphatase and alkaline phosphatase. In an investigation of the in vitro metabolism of OPC-61815 by human liver S9 fraction and human hepatocytes, all metabolites detected were the same as those of OPC-41061, and no metabolite with a phosphate group was detected in the metabolic reaction of (^{14}C)-OPC-61815 with human liver S9 fraction.

Following a single IV dose of (^{14}C)-OPC-61815 at 12.75 mg/kg to male and female rats, the urinary and fecal excretion of radioactivity up to 168 hours postdose was 4.59% and 91.08%, respectively, in male rats, and 4.74% and 93.26%, respectively, in female rats, showing that the radioactivity administered was excreted mainly in feces. The biliary excretion of radioactivity was 92.2% in male rats and 91.5% in female rats. In male rats, 61.0% of the radioactivity administered was resorbed via enterohepatic circulation. No obvious sex difference was noted in urinary, fecal, or biliary excretion in rats. Following

a single IV dose of (¹⁴C)-OPC-61815 at 3.825 mg/kg to male dogs, the urinary and fecal excretion of radioactivity up to 168 hours postdose was 5.32% and 89.50%, respectively.

2.4 Summary of Clinical Experience

2.4.1 Safety

In a Phase I single IV dose trial in healthy male adults (protocol No.: 263-08-001), OPC-61815 at 0.3, 1, 3, 7.5, 15, or 30 mg or placebo was administered intravenously over 5 minutes to 54 subjects. Twenty-four adverse events (AEs) occurred in 13 of 36 subjects (36.1%) in the OPC-61815 group, and 12 AEs occurred in 5 of 18 subjects (27.8%) in the placebo group. The AEs that occurred in at least 2 subjects in the OPC-61815 group were 2 occurrences each of ventricular extrasystoles, abdominal pain, and blood cholesterol increased. Of these all but 1 case of abdominal pain, were considered to be potentially drug-related treatment-emergent AEs (TEAEs). All AEs in this trial were mild in severity and resolved with or without treatment. The above results demonstrated that a single IV dose of OPC-61815 at 0.3 to 30 mg is well-tolerated in healthy male adults.

In a Phase I multiple IV dose trial in healthy male adults (protocol No.: 263-09-001), OPC-61815 at 1.25, 5, or 20 mg or placebo was administered intravenously over 1 minute to 36 subjects. After receiving a single dose, subjects were given a 1-day dose intermission and then received multiple once-daily IV doses for 7 days. In total, 168 AEs occurred in 24 of 27 subjects (88.9%) in the OPC-61815 group and 5 AEs occurred in 4 of 9 subjects (44.4%) in the placebo group. The AEs reported in at least 3 subjects in the OPC-61815 group were as follows: 39 occurrences of feeling abnormal in 9 subjects, 31 occurrences of pruritus in 5 subjects, 5 occurrences of blood uric acid increased in 5 subjects, 4 occurrences of diarrhoea in 4 subjects, 24 occurrences of pruritus generalized in 3 subjects, 8 occurrences of erythema in 3 subjects, and 4 occurrences of bradycardia in 3 subjects. Of these events, 38 occurrences of feeling abnormal in 8 subjects, 5 occurrences of blood uric acid increased in 5 subjects, 30 occurrences of pruritus in 4 subjects, 24 occurrences of pruritus generalized in 3 subjects, 8 occurrences of erythema in 3 subjects, 16 occurrences of hypoesthesia in 2 subjects, 2 occurrences of diarrhea in 2 subjects, 9 occurrences of nausea in 2 subjects, and 7 occurrences of pruritus genital in 1 subject were judged to be potentially drug-related TEAEs. No deaths or other serious potentially drug-related TEAEs were observed. All AEs reported in the OPC-61815 group were mild or moderate in severity and resolved without treatment. The results demonstrated that OPC-61815 is well-tolerated in healthy male adults when administered intravenously once daily for 7 days at up to 20 mg. However, based on the fact that potentially drug-related TEAEs that did not occur after oral administration of OPC-41061, such as feeling abnormal, pruritus, and erythema, occurred with a high

incidence during or immediately after repeated administration of OPC-61815; OPC-61815 solution was suspected to be involved in the occurrence of such potentially drug-related TEAEs.

In order to explore causes of the potentially drug-related TEAEs and explore the injection duration able to reduce the occurrence of these potentially drug-related TEAEs, a Phase I IV infusion rate trial (protocol No.: 263-10-005) was conducted. A single dose of OPC-61815 at 7.5 or 15 mg or placebo was administered intravenously over 2 hours, 5 minutes, or 1 minute to healthy male adult subjects. Adverse events occurred in 6 of 12 subjects in the OPC-61815 group and 5 of 6 subjects in the placebo group after administration over 2 hours; 10 of 12 subjects in the OPC-61815 group and 3 of 6 subjects in the placebo group after administration over 5 minutes; and 10 of 12 subjects in the OPC-61815 group and 4 of 6 subjects in the placebo group after administration over 1 minute. All the AEs reported were mild or moderate in severity. Adverse events (feeling abnormal, feeling hot, erythema, hyperhidrosis, pruritus, rash, urticaria, nausea, epigastric discomfort, and dyspnea) similar to feeling abnormal, pruritus, or erythema, which occurred with a high incidence in the multiple IV dose trial of OPC-61815 (protocol No.: 263-09-001) were extracted as AEs of special interest (AESI). Adverse events of special interest were reported in 1 of 12 subjects in the OPC-61815 group and 3 of 6 subjects in the placebo group after administration over 2 hours (pruritus, rash, urticaria, and feeling abnormal). A relationship to the trial drug was ruled out for AEs that occurred in 1 subject (rash) in the OPC-61815 group and 2 subjects in the placebo group (feeling abnormal and urticaria), out of the above AEs. After administration over 5 minutes, AESIs were reported in 9 of 12 subjects in the OPC-61815 group and 2 of 6 subjects in the placebo group (dyspnea, erythema, hyperhidrosis, pruritus, feeling abnormal, and feeling hot). All these AEs were assessed as related to the trial drug. After administration over 1 minute, AESIs were reported in 10 of 11 subjects in the OPC-61815 group and 4 of 6 subjects in the placebo group (nausea, epigastric discomfort, erythema, hyperhidrosis, pruritus, feeling abnormal, and feeling hot). All these AEs, except for 1 event (erythema) in the OPC-61815 group, were assessed as related to the trial drug. All potentially drug-related TEAEs occurred during or immediately after IV dosing, and most of them resolved without treatment within 10 minutes of the start of trial drug administration. There were no clinically significant changes from baseline in plasma histamine concentration. As shown above, causes of AESIs remained unknown.

2.4.2 Pharmacokinetics

Pharmacokinetic data for OPC-61815 free form following single and multiple IV doses is presented in the table below. The PK data for OPC-61815 free form following 1- and 5-minute infusions is available in the IB¹, along with PK data for OPC-41061 and major metabolites for all studies.

Table 2.4.2-1 Pharmacokinetic Data for OPC-61815 Free Form

| Dose (mg) | AUC _∞ (ng.h/mL) | AUC _t (ng.h/mL) | C _{max} (ng/mL) | t _{max} (h) ^a | t _{1/2} (h) |
|--|-------------------------------|-------------------------------|-----------------------------|--------------------------------------|-------------------------|
| Single IV dose – Mean (SD) | | | | | |
| 0.3 mg | - | 7.803 (8.170) | 53.02 (29.28) | 0.020 (0-0.25) | - |
| 1 mg | 175.0 (-) | 85.90 (21.91) | 182.2 (21.72) | 0.000 (0-0.25) | 0.7170 (0-0) |
| 3 mg | 427.2 (61.14) | 374.3 (52.91) | 559.5 (85.52) | 0.000 (0-0.02) | 0.6335 (0.1065) |
| 7.5 mg | 1242 (182.2) | 1144 (171.1) | 1832 (294.2) | 0 (0-0) | 1.172 (0.2819) |
| 15 mg | 3008 (416.6) | 2868 (362.3) | 3348 (637.7) | 0.000 (0-0.25) | 1.730 (0.3279) |
| 30 mg | 4882 (817.9) | 4727 (839.9) | 7670 (755.3) | 0 (0-0) | 1.683 (0.4837) |
| Multiple IV dose – Day 1: Mean (SD) | | | | | |
| 1.25 mg | 211.8 (32.11) | 167.3 (32.55) | 371.8 (78.15) | 3.0 (3-3) | 0.5308 (0.1074) |
| 5 mg | 886.7 (140.8) | 784.0 (150.2) | 1165 (394.4) | 3.0 (3-15) | 1.193 (0.3741) |
| 20 mg | 3379 (492.8) | 3178 (400.1) | 4351 (1496) | 3.0 (3-15) | 2.510 (1.927) |
| Multiple IV dose – Day 9: Mean (SD) | | | | | |
| 1.25 mg | 169.0 (33.05) ^b | - | 320.0 (89.42) | 3.0 (3-15) | 0.5748 (0.1549) |
| 5 mg | 924.8 (136.9) ^b | - | 1375 (368.4) | 3.0 (3-3) | 1.329 (0.4530) |
| 20 mg | 3416 (344.7) ^b | - | 4137 (955.7) | 3.0 (3-15) | 2.419 (1.145) |

Abbreviations: AUC_∞ = area under the concentration-time curve from time zero to infinity; AUC_t = area under the concentration-time curve calculated to the last observable concentration at time t; AUC_{24h} = area under the concentration-time curve from time zero until 24 hours postdose; C_{max} = maximum peak concentration; IV = intravenous; t_{max} = time to maximum peak concentration; t_{1/2} = elimination half-life.

^a median (min-max)

^b AUC_{24h}

2.5 Known and Potential Risks and Benefits

Healthy subjects in the current trial will not receive any health benefit (beyond that of an assessment of their medical status) from participating in the trial. The risks of participation are primarily those associated with adverse reactions to the trial treatment

and the IV doses, although there may also be some discomfort from collection of blood samples and other trial procedures.

No deaths or other serious adverse events (SAEs) were reported in the Phase I trials of OPC-61815 in healthy adult male subjects (263-08-001, 263-09-001, and 263-10-005). Feeling abnormal, feeling hot, erythema, hyperhidrosis, pruritus, rash, urticaria, nausea, epigastric discomfort, and dyspnea were frequently reported following IV dosing of OPC-61815 in Trials 263-09-001 and 263-10-005, and were considered AESIs. In Trial 263-10-005, 1- and 5-minute administrations were associated with frequent occurrences of AESIs in OPC-61815-treated subjects, whereas following a 2-hour administration, only 1 subject experienced an AESI, and this was considered unrelated to trial drug. These findings suggest that a longer duration of OPC-61815 administration would reduce the risk of developing these events.

All potentially trial drug-related AEs reported in completed Phase I trials occurred during or immediately after trial drug administration. Most events spontaneously resolved within 10 minutes after start of trial drug administration, subjects should be closely monitored for skin symptoms following start of trial drug administration.

More information about the known and expected benefits, risks, and reasonably anticipated AEs associated with OPC-61815 may be found in the IB.¹

The trial site will receive updated versions of the IB, when available, and the trial site should refer to the most current version as needed.

3 Objectives and Endpoints

| Table 3-1 Trial Objectives and Endpoints | |
|--|--|
| Objectives | Endpoints |
| 
Primary:
 
To determine the mass balance of total radioactivity following a single IV infusion of (¹⁴C)-OPC-61815.
 
To determine routes and rates of elimination of total radioactivity following a single IV infusion of (¹⁴C)-OPC-61815.
 
To assess the PK of total radioactivity in plasma and whole blood following a single IV infusion of (¹⁴C)-OPC-61815.
 | 
The PK parameter endpoints for OPC-61815 free form and OPC-41061 in plasma, and total radioactivity in whole blood and plasma, and the PK parameter endpoints for total radioactivity in urine and feces are detailed in Section 9.4.3.2.
 |

| | |
|---|--|
| To assess the PK of OPC-61815 free form and OPC-41061 in plasma following a single IV infusion of (¹⁴ C)-OPC-61815. To identify and characterize metabolites in plasma, urine, and feces following a single IV infusion of (¹⁴ C)-OPC-61815. | Metabolic profile of (¹⁴ C)-OPC-61815 and identification of radiolabeled metabolites present at >10% of the total drug-related exposure (AUC) plasma. |
| Secondary: To assess the safety and tolerability of a single IV infusion of (¹⁴ C)-OPC-61815. | Adverse events, clinical laboratory evaluations, physical examination findings, vital signs (blood pressure, pulse rate), body weight, and 12-lead electrocardiogram parameters. |

[Section 9.4](#) describes the statistical analysis of the endpoints.

4 Trial Design

4.1 Type/Design of Trial

This will be a Phase I, single-site, open-label, nonrandomized, single IV dose trial in healthy male Japanese subjects.

Potential subjects will be screened to assess their eligibility to enter the trial within 28 days prior to the dose administration. Subjects will be enrolled and admitted into the trial site on Day -1. On Day 1, all subjects will receive a single IV infusion of 16 mg (¹⁴C)-OPC-61815, containing approximately 75.1 μ Ci (2.78 MBq), over 60 minutes (55 to 65 minutes, inclusive) in the fasted state.

It is planned for at least 8 subjects to be dosed to ensure that 6 subjects complete the IV infusion. Up to a maximum of 10 subjects will be dosed in total.

An overview of the trial design is shown in [Figure 1.2-1](#).

Subjects will be confined to the trial site until at least Day 9. Subjects will be discharged from the trial site on Day 9 if the following discharge criteria are met:

- $\geq 90\%$ mass balance recovery, and/or
- < 1% of the total radioactive dose is recovered in combined excreta (urine and feces) in 2 consecutive 24-hour periods.

If these criteria are not met by Day 9, subjects will remain at the trial site until any one of the discharge criterion are met up to a maximum of Day 10 to continue 24-hour blood,

urine, and feces collections for total radioactivity, unless otherwise agreed upon by the sponsor and investigator.

If criteria are not met by Day 10, subjects may be asked to collect 24-hour excreta samples on up to 2 further occasions on a nonresidential basis to allow extrapolation of urinary and fecal excretion. If needed, the 2 additional 24-hour nonresidential collections will start on Days 10 and 11 (to be brought to the trial site at the end of the collection interval on Days 11 and 12, respectively). If on the second occasion the subject has still not met the desired criterion, then the subject will be discharged from the trial, per investigator and sponsor decision.

Final Discharge from trial will be day of discharge from residential treatment period or the day of last outpatient visit if required to attend them based on the discharge criteria. The total duration of trial participation for each subject (from Screening through Final Discharge from trial) is anticipated to be a maximum of approximately 40 days.

The start of the trial is defined as the date the first enrolled subject signs an informed consent form (ICF). The point of enrollment occurs at the time of subject number allocation. The end of trial is defined as the last date of contact or the date of final contact attempt for the last subject completing or withdrawing from the trial.

A Schedule of Assessments is presented in [Table 1.3-1 \(Section 1.3\)](#).

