1.3 Schedule of Assessments

| Table 1.3-1 | | Schedule of Assessments | | | | |
|---|-----------------------------------|-------------------------|--|----------------|--|--|
| Period | Screening Day -28 to Day -2 | Check-in Day -1 | Days 1 to 8 | | Discharge ^a Days 9 to 10 | Outpatient Visits ^b Days 11 to 12 |
| ENTRANCE/HISTORY | | | | | | |
| Informed consent | X | | | | | |
| Demographics | X | | | | | |
| Inclusion/Exclusion Criteria | X | X | | | | |
| Medical history | X | X ^c | | | | |
| Urine drug screen | X | X | | | | |
| Alcohol breath test | X | X | | | | |
| Serology | X | | | | | |
| Height and body weight | X ^d | X ^e | 24 and 48 hours after the start of infusion ^e | | | |
| INVESTIGATIONAL MEDICINAL PRODUCT ADMINISTRATION | | | | | | |
| (¹⁴ C)-OPC-61815 | | | Day 1 (0 hours) | | | |
| PHARMACOKINETICS | | | | | | |
| Blood sampling for OPC-61815 free form and OPC-41061 concentration (plasma) | | | Predose and 1 hour (end of infusion), and 1.5, 2, 3, 4, 6, 12, 24, and 48 hours after the start of infusion | | | |
| Blood sampling for total radioactivity (whole blood and plasma) | | | Predose and 1 hour (end of infusion), and 1.5, 2, 3, 4, 6, 12, 24, 48, 72, 96, 120, 144, and 168 hours after the start of infusion | X ^a | | |

Table 1.3-1 Schedule of Assessments

| | | | | | |
|--|---|----------------|---|-------------------|----------------|
| Blood sampling for metabolite profiling and identification (plasma) | | | Predose and 1 hour (end of infusion), and 1.5, 2, 3, 4, 6, 12, 24, 48, 72, 96, 120, 144, and 168 hours after the start of infusion | | |
| Urine collection for total radioactivity and metabolite profiling and identification | | | Predose (from Check-in to 0 hours) and 0 to 24, 24 to 48, 48 to 72, 72 to 96, 96 to 120, 120 to 144, and 144 to 168 hours after the start of infusion | X ^a | X ^b |
| Feces collection for total radioactivity and metabolite profiling and identification | | | Predose (from Check-in to 0 hours) and 0 to 24, 24 to 48, 48 to 72, 72 to 96, 96 to 120, 120 to 144, and 144 to 168 hours after the start of infusion | X ^a | X ^b |
| SAFETY | | | | | |
| Adverse event recording | X | X | Ongoing | X | X |
| Prior/concomitant medication monitoring | X | X | Ongoing | X | X |
| Clinical laboratory evaluations | X | X | 1.5 ⁱ , 24, and 48 hours after start of infusion | X ^g | |
| Physical examination | X | X ^f | 1.5, 24, and 48 hours after start of infusion ^f | X ^{f, h} | |

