| Supine blood pressure and pulse rate | X | X | 1.5, 24, and 48 hours after the start of infusion | X ^h | |
| Oral body temperature | X | | | | |
| 12-lead electrocardiogram | X | X | 24 and 48 hours after the start of infusion | X ^g | |

^a Subjects can be discharged on Day 9 if the following discharge criteria are met: $\geq 90\%$ mass balance recovery and/or $< 1\%$ of the total radioactive dose is recovered in combined excreta (urine and feces) in 2 consecutive 24-hour periods. If the discharge criteria are not met, subjects will be asked to remain resident within at the trial site and additional 24-hour collection (blood, urine, and feces) for total radioactivity will continue until these criteria are met, up to a maximum of Day 10.

^b Up to 2 additional 24-hour nonresidential collections (urine and feces) for total radioactivity may occur if discharge criteria have not been met by Day 10. Subjects will collect excreta samples at home for the 24-hour period prior to the clinic visit and deliver them to the trial site at the end of the collection interval, within 24 hours.

^c Interim medical history.

^d Height measured at Screening only.

^e Weight only.

^f Symptom-directed physical examination.

^g Day 9.

^h Only on day of Discharge.

ⁱ At this time point only blood samples will be taken for clinical laboratory evaluation.

| Table 1.3-2 Time Windows for Assessments | | | |
|---|------------|---|--|
| Item | Day | Time point relative to start of infusion (h) | Window |
| Blood sampling for Pharmacokinetics | 1 | predose | Within 2 hours of IMP administration |
| | | 1 | Within 2 minutes after end of IMP administration |
| | | 1.5 | Specified time point \pm 2 minutes |
| | | 2 | Specified time point \pm 3 minutes |
| | | 3 | Specified time point \pm 5 minutes |
| | | 4 | Specified time point \pm 10 minutes |
| | | 6, 12 | Specified time point \pm 15 minutes |
| | 2 | 24 | Specified time point \pm 30 minutes |
| | 3 | 48 | Specified time point \pm 30 minutes |
| | 1 | 1.5 | Specified time point \pm 10 minutes |
| Clinical laboratory evaluations | 2 | 24 | Specified time point \pm 120 minutes |
| | 3 | 48 | Specified time point \pm 120 minutes |
| | 1 | 1.5 | Specified time point \pm 10 minutes |
| Physical examination | 2 | 24 | Specified time point \pm 60 minutes |
| | 3 | 48 | Specified time point \pm 60 minutes |
| | 1 | 1.5 | Specified time point \pm 10 minutes |

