5.2.1 Inclusion Criteria

Subjects are required to meet all of the following criteria at the Screening visits, unless otherwise stated:

- 1) Male subjects between 35 and 55 years of age, inclusive.
- 2) Hold a valid Japanese passport and be first-generation Japanese, defined as the subject, the subject's biological parent, and all of the subject's biological grandparents being of exclusive Japanese descent, have been born in Japan, and not lived outside of Japan for more than 5 years.
- 3) Body mass index between 18.5 to 28.0 kg/m² (inclusive); and a total body weight between 50 and 100 kg, inclusive.
- 4) In good health, determined by no clinically significant findings from medical history, physical examination, 12-lead ECG, vital sign measurements, and clinical laboratory evaluations (congenital nonhemolytic hyperbilirubinemia [eg, suspicion of Gilbert's syndrome based on total and direct bilirubin] is not acceptable) at Screening and Check-in as assessed by the investigator (or designee).
- 5) Subjects will agree to use contraception as detailed in [Section 10.4](#).
- 6) Able to comprehend and willing to sign an ICF and to abide by the trial restrictions.
- 7) History of a minimum of 1 bowel movement per day.

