5.3.1 Meals and Dietary Restrictions

While confined at the trial site, subjects will receive a standardized, high-fiber diet at scheduled times that do not conflict with other trial-related activities. Prune juice may be administered on an as-needed basis to aid in normal bowel function and will not be considered a concomitant medication. Subjects will be fasted overnight (at least 8 hours) before collection of blood samples for clinical laboratory evaluations.

Foods and beverages containing poppy seeds, grapefruit, star fruit, or Seville oranges will not be allowed from 7 days prior to Check-in until Final Discharge from trial.

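### The <1% discharge criterion does not require a stool in the two 24-hour periods, so a subject below 90% recovery can, rarely, end excreta collection because nothing was passed

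*Protocol*

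**What the plan says.** Protocol 4.1 gives two discharge criteria joined by and/or: at least 90% recovery, or less than 1% "of the total radioactive dose is recovered in combined excreta (urine and feces) in 2 consecutive 24-hour periods". A subject who meets neither by Day 9 stays "until any one of the discharge criterion are met up to a maximum of Day 10", so one criterion is sufficient. The rule is repeated in the Synopsis (1.1), footnote a of the Schema (1.2), footnote a of Table 1.3-1, and SAP Section 4 with footnote a of its Figure 1. The footnotes are permissive ("Subjects can be discharged on Day 9 if the following discharge criteria are met"), whereas the text of Protocol 4.1 says that such subjects will be discharged.

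Scheduled excreta intervals for everyone end with "120 to 144, and 144 to 168 hours after the start of infusion". Day 10 residence and the outpatient collections apply only while the criteria are unmet, and discharge from residence is otherwise Final Discharge.

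On route, Protocol 2.3 reports for male dogs that "the urinary and fecal excretion of radioactivity up to 168 hours postdose was 5.32% and 89.50%, respectively". The rat values are 4.59% urine and 91.08% feces (males), and 4.74% and 93.26% (females).

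Several provisions favor regular stools: an entry criterion, "History of a minimum of 1 bowel movement per day"; a high-fiber diet; and, in Protocol 5.3.1, "Prune juice may be administered on an as-needed basis to aid in normal bowel function". None of them is part of the discharge rule.

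**The concern.** A low-excretion rule is meant to show that excretion has ended. When nearly all of the label leaves in feces, two periods without a stool look the same to this rule as two periods in which nothing was left to excrete. Urine alone is then too small to keep the subject in collection.

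Mass balance and routes of elimination are the first two primary objectives. In an affected subject, total recovery and percent of dose in feces are both too low, and the missing label cannot be recovered later. Protocol 7.4.1 provides for replacing only subjects who do not complete the infusion. Protocol 9.3 leaves missing data to the SAP, which has a general no-imputation rule (8.1.1) and nothing on stool-free intervals.

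**Working it through.** The plan gives no figure to reproduce for this rule, and no human excretion kinetics. The following is an illustration on stated assumptions.

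**Inputs from Protocol 2.3:** dog urine 5.32% and feces 89.50%, total 94.82%, taken as amounts excreted by 168 h.

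**Assumptions:** one excretion half-life T for both routes; each stool clears everything that has reached the bowel; no stool from 120 to 168 h; days independent, with daily stool probability p.

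**Formulas.** Let s = 1/(1 − 2^(−168/T)), which fixes the 168 h total with daily stools at 94.82%.

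- Recovery at 168 h, no stool 120–168 h: s × 89.50 × (1 − 2^(−120/T)) + 5.32
- Recovery at 192 h with a stool: s × 94.82 × (1 − 2^(−192/T))

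**At T = 36 h,** s = 1.041.

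- Feces at 168 h: 1.041 × 89.50 × (1 − 0.0992) = 83.9%. Total 83.9 + 5.3 = 89.2%, which is below 90%.
- Urine in 120–144 h and 144–168 h: 0.20% and 0.13%. The <1% criterion is met whether it is read per period or summed over both.
- With a stool, the 192 h total is 1.041 × 94.82 × (1 − 0.0248) = 96.3%, of which feces are 90.9%.
- Loss against a 192 h stop: 7.0 points. Against a peer with daily stools who stops at 168 h: 94.8 − 89.2 = 5.6 points.
- In the mean, the 7.0 points become 7.0/8 = 0.9 or 7.0/6 = 1.2; the 5.6 points become 0.7 or 0.9.
- Feces as a share of recovered label: 94.0% instead of 94.4%.

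**Which half-lives matter**

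| T (h) | 168 h, no stool 120–168 h | 192 h, with stool |
|---|---|---|
| 24 | 92.7% | 95.2% |
| 30 | 91.0% | 95.7% |
| 34 | 89.8% | 96.1% |
| 36 | 89.2% | 96.3% |

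Recovery falls below 90% from T = 33.4 h. The implied final total, s × 94.82, reaches 100% of dose at T = 39.3 h. On the dog values the window is therefore about 33–39 h. On the male-rat total (95.67%) it is 36.0–37.1 h. On the female-rat total (98.00%) there is none, because the two limits are 43.8 and 29.8 h.

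**How often, at T = 36 h.** All daily stool patterns to 264 h were enumerated, comparing the current rule with the proposed one. The figures are the chance per subject that the current rule recovers at least 1 point less.

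| Decision uses excreta to | p = 95% | p = 90% | p = 80% |
|---|---|---|---|
| 168 h | 0.25% | 1.0% | 4.0% |
| 192 h | 0.01% | 0.1% | 0.8% |

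The first row is essentially (1 − p)², for example 0.10² = 1.0%. In the second row, two stool-free days (144–192 h) still leave recovery at 92.7%, so three are needed: 0.10³ = 0.1%. The expected bias in the mean for the 168 h decision is 0.02, 0.08 and 0.35 point.

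Pairs of periods that are not the most recent add nothing at half-lives of 24–48 h, so it is the stool condition that matters.

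**The case against.** The strongest reply is that the documents' own data leave little room for harm. Protocol 2.3 says of rats: "At 168 hours postdose, the concentrations of radioactivity were below the lower limit of quantification in almost all tissues". The half-life window is narrow on the dog values, narrower on the male-rat values and empty on the female-rat values. The frequencies above are conditional on a half-life inside that window, and the chance of that is unknown. This stands, and it limits the point to a small one.

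Second, 168–192 h may well be collected before anyone leaves. Subjects are resident until at least Day 9. Table 1.3-1 marks excreta collection under Days 9 to 10, and Table 10.3-1 allows 16 radioactivity blood samples against 15 scheduled to 168 h. However, footnote a ties the extra collection to unmet criteria, so the documents do not settle the matter. Both rows of the frequency table should be kept.

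Third, similar losses can occur through the other criterion. At half-lives of 30 and 33 h the same missed stools give 91.0% and 90.1%, which is 4.7 and 5.8 points below a 192 h stop, and those subjects leave on the 90% rule. The fix does not touch this.

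Fourth, SAP 3.1 already reports excretion per sampling interval, so two empty fecal intervals would be visible. That makes the shortfall explainable but does not recover the label.

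Finally, Protocol 8.2.2 places collection procedures in a separate document, which may already deal with stool-free periods.

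A reader might infer much larger losses at longer half-lives, such as 48–72 h. The documents do not support that: the dog values are amounts up to 168 h, and above 39.3 h they would imply more than 100% of the dose excreted.

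**Conclusion.** The gap in the rule is real: either criterion suffices, no section requires a stool, and with mainly fecal excretion two stool-free days can meet the <1% criterion while label is still to come. Its practical weight is low: a rare event, costing an affected subject 7.0 points against a 192 h stop or 5.6 against a peer stopping at 168 h, and about 1 point in a mean of 6 to 8.

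These sizes rest on human excretion resembling the dog values, on a half-life near 36 h, and on assumed stool probabilities. At 24 h the subject is already above 90% after two missed days.

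A reader might conclude that the mass balance result or the elimination route is in doubt. It is not: feces remain about 94% of recovered label either way, and collection to 168 h is scheduled for everyone. This is a cheap improvement to a stopping rule, not a defect that threatens the primary objectives.

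**What to change.** In Protocol 4.1, and wherever the rule is repeated (Protocol 1.1, 1.2 footnote a and Table 1.3-1 footnote a; SAP Section 4 and Figure 1 footnote a), state that the <1% criterion counts only for the two most recent consecutive 24-hour periods, and only if at least one fecal sample was obtained in them. Otherwise continue with the Day 10 and outpatient collections already allowed, with the present caps unchanged. The words on recency are a clarification. If the separate procedures document already has a stool rule, a cross-reference is enough.

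The cost is wording plus an extra day or an outpatient collection for subjects below 90% with no stool in both periods. At Day 9 that is at most about 0.25%, 1% or 4% of subjects at 95%, 90% or 80% daily stool probability. Some of them will in fact have finished excreting. Sample size and analysis do not change.
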